#### 7.2 Source Documents

Source data is all information, original records of clinical findings, observations, or other activities in a clinical trial necessary for the reconstruction and evaluation of the trial. Source data are contained in source documents. Examples of these original documents, and data records include: hospital records, clinical and office charts, laboratory notes, memoranda, subjects' diaries or evaluation checklists, pharmacy dispensing records, recorded data from automated instruments, copies or transcriptions certified after verification as being accurate and complete, microfiches, photographic negatives, microfilm or magnetic media, x-rays, subject files, and records kept at the pharmacy, at the laboratories, and at medico-technical departments involved in the clinical trial. Source documents will be stored as outline in "Confidentiality" in section 7.1 above.

# 7.3 Case Report Forms

The Montefiore Electronic Medical Record will be used as the primary data collection instrument for the study.

# 8.0 Data Safety and Monitoring Boards

A Data Safety Monitoring Committee is being convened by [name]. They will have the responsibility for ensuring data and safety monitoring along with the PI who is ultimately responsible for the ongoing monitoring and safety of clinical protocols. The primary functions of this DSMC are as follows:

- To review and ensure protocol compliance with dose escalation in phase I trials
- 2. To review/assure protocol compliance for all trials that have two-stage phase II designs,
- Reviewing all internal and external serious adverse reports, investigator alerts, action letters, and other safety reports for trials being performed at AECC-affiliated institutions and;
- 4. To implement and to determine the adequacy of DSM plans of all approved protocols.

The committee will meet quarterly or more frequently as needed. This committee lead by [name] will review serious (grade 3 or higher) adverse events from this study. In the event that the DSMC decides that a revision is warranted, the committee will immediately notify the principal investigator of this study. The DSMC has the authority to close trials to patient accrual should the risk to patients be excessive or outweigh the potential benefits of the study. All study

suspensions and closures will be forwarded to the IRB/CCI and study sponsor from the DSMC.

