# 4.3 Study Endpoints

The primary endpoint of this study is safety, defined as the absence of any treatment-related Grade ≥3 adverse events during radiotherapy or within 3 months of radiotherapy completion, scored using CTCAE version 4.0.[6] Secondary study endpoints include:

# Optional

- Quality of Life
  - Improvement in NIH Patient-Reported Outcomes Measurement Information System (PROMIS) measures, including pain interference and physical functioning at 3 months (and optionally at 6 months and 12 months) after treatment[7, 8]
    - A one point change, either positive (improvement) or negative (decline), will be considered to be clinically meaningful[9]
- Inflammation as measured by ultrasound.
  - Noninvasive imaging, such as ultrasound (US), allows for an objective assessment of subclinical disease activity.
  - Anechoic area will be measured in the dermis before and after treatment, as well as other sonographic criteria of HS [10](See Appendix for Sonographic Scoring and Diagnosis of HS)
  - As there are no validated ultrasound criteria to measure clinical improvement, reduction in anechoic areas and sonographic criteria will be calculated. It is estimated that the treatment will induce a 50% reduction in the anechoic area.
  - Anechoic areas and other sonographic criteria will be correlated with PROMIS scores and Hurley Staging.
- Evaluation of cutaneous discharge
  - Swabs will be collected from discharge and sent for fluid count, which will include evaluation of infiltrating leukocytes from the discharge.
- Immunohistochemical Evaluation of HS Tissue Biopsies
  - Tissue biopsies will be collected before and after treatment. Tissue sections will be evaluated by H&E as well as immunohistochemistry for infiltrating leukocytes and other cells, such as T cells, B cells, plasma cells, dendritic cells, macrophages, and keratin. Image J will be used to quantify cells in a standard manner for comparison before and after treatment.

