#### 5.0 STATISTICAL CONSIDERATIONS

A maximum of 20 patients will be enrolled into the study. The accrual rate is expected to be 1-2 patients per month based on the volume of patients with stage 2-3 HS treated within the Montefiore Hidradenitis Suppurativa Treatment Center. An early stopping rule for safety will be implemented as follows based on Simon's optimal two-stage design. After the first 6 patients have been enrolled, accrual will be temporarily suspended while these patients are monitored for occurrence of treatment-related grade ≥ 3 toxicity for 3 months. At the end of 3

months, results will be sent to the DSMB for further evaluation. The trial will be terminated early if more than 1 patient experiences grade  $\geq$  3 treatment related toxicity or any patient experiences grade 4 toxicity. Otherwise, upon approval from the DSMB, the second phase of recruiting will be initiated. If 1 or fewer grade  $\geq$  3 toxicities and 0 grade 4 toxicities are observed, the trial will continue until a total of 20 patients have been evaluated. At the end of the trial, the treatment will be considered safe and worthy of further study if no more than 3 patients experience grade  $\geq$  3 treatment related toxicity and none experience grade 4 treatment related toxicity.

The target Grade  $\geq$  3 toxicity rates is no more than 10%, and a toxicity rate greater than 30% is considered clinically unacceptable. The design specified above has the following operating characteristics. The probability of accepting the treatment for further study if the toxicity rate is unacceptably high (> 30%) is at most 10%. In contrast, there is an 80% probability of accepting the treatment for further study if the toxicity rate is less than 10%. In addition, if 0 out of 20 patients experience Grade 4 toxicity at the end of the study, we will be able to conclude with 95% confidence that the true Grade 4 toxicity rate is not greater than 17%.

The proportion of patients who have treatment-related toxicity will be computed, along with exact 95% confidence intervals. Since the study is a phase I trial, we will NOT do any hypothesis testing or models, The study will present the descriptive summary statistics for each outcomes. Biomarker levels measured at different time points and other continuous variables will be summarized by computing means, medians, standard deviations and ranges.

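### The Grade ≥3 safety counts and the only planned toxicity proportion are limited to treatment-related events, yet no one is named to decide relatedness and no all-cause figure is planned

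*Combined protocol and SAP*

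**What the plan says.** Section 4.3 makes safety the primary endpoint, "defined as the absence of any treatment-related Grade ≥3 adverse events during radiotherapy or within 3 months of radiotherapy completion". Section 5.0 carries the same restriction into the decision rule. The first 6 patients are watched for "treatment-related grade ≥ 3 toxicity for 3 months". "The trial will be terminated early if more than 1 patient experiences grade" ≥3 treatment-related toxicity, the trial stops. At the end, no more than 3 of 20 patients may have such toxicity. For reporting, Section 5.0 says: "The proportion of patients who have treatment-related toxicity will be computed, along with exact 95% confidence intervals". No other toxicity proportion is named.

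Section 8.0 says the committee "will review serious (grade 3 or higher) adverse events from this study". It shares monitoring "along with the PI who is ultimately responsible for the ongoing monitoring and safety of clinical protocols", and it may close accrual. Attribution is not mentioned. Sections 4.1 and 5.0 send the interim results to the DSMB and require its approval before stage 2. (Section 8.0 says DSMC; I read the two names as one body.) Neither section describes a board step for the final verdict.

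Sections 9.1 and 9.2 refer adverse event definitions and IRB reporting to an institutional policy that is not part of the documents.

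**The concern.** The trial has a single arm, so no control group shows how often Grade ≥3 skin events occur without radiotherapy. Section 2.1 describes HS as causing painful abscesses, sinus tracts and scarring. Appendix B lists skin pain, induration and ulceration among the relevant toxicities. Eligible patients have Hurley stage 2-3 disease and have failed, or cannot have, standard treatment. A new Grade 3 skin event within 3 months of radiotherapy could therefore reasonably be put down to either cause.

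The relatedness label decides whether such a patient enters the Grade ≥3 count. The documents do not say who applies it, by what criteria, or who checks it. If Section 5.0 is followed as written, the reported proportion will not show how many Grade ≥3 events were set aside as unrelated, so a reader cannot check the verdict.

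**Working it through.** **Inputs, all from Section 5.0.** Stage 1: 6 patients, continue if at most 1 has related Grade ≥3 toxicity. Total: 20 patients, accept if at most 3 do. Unacceptable rate 30%, target rate 10%. Stated acceptance: at most 10% at the 30% rate and 80% at the 10% rate. The Grade 4 clause is left out, as the stated figures appear to do; including it would lower every acceptance probability.

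**Formula.** P(accept | p) = Σ over x = 0, 1 of P(Bin(6, p) = x) × P(Bin(14, p) ≤ 3 − x).

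**The plan's own figures.**
- p = 0.30: 0.1176 × 0.3552 + 0.3025 × 0.1608 = 0.0418 + 0.0487 = 0.090 (stated: at most 10%).
- p = 0.10: 0.5314 × 0.9559 + 0.3543 × 0.8416 = 0.5080 + 0.2982 = 0.806 (stated: 80%).

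Both reproduce.

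**How often one patient is decisive (no misattribution rate needed).** A trial is one patient beyond a limit if it has exactly 2 of 6 at stage 1, or passes stage 1 and ends on exactly 4 of 20.

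| True rate | Exactly 2 of 6 | Passes, then exactly 4 of 20 | Sum |
|---|---|---|---|
| 10% | 9.8% | 5.9% | 15.7% |
| 20% | 24.6% | 14.3% | 38.9% |
| 30% | 32.4% | 8.6% | 41.0% |

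The two cases differ in effect. Relabelling at 4 of 20 turns non-acceptance into acceptance. Relabelling at 2 of 6 only lets the trial continue. At a true 30% rate, acceptance would still need at most 2 further events in 14 patients: 0.3241 × 0.1608 = 5.2%.

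The exact 95% intervals for 3/20 (3.2% to 37.9%) and 4/20 (5.7% to 43.7%) overlap almost entirely, although the verdict differs.

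**Illustration: related events labelled as HS.** The documents give no misattribution rate, so this share is assumed. If a share m of patients with a related event is labelled HS, the counted rate is 0.30 × (1 − m).

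| m (assumed) | Counted rate | P(accept) at a true 30% |
|---|---|---|
| 0% | 0.30 | 9.0% |
| 10% | 0.27 | 14.5% |
| 20% | 0.24 | 22.1% |
| 30% | 0.21 | 32.1% |

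**Illustration: HS events counted as related.** Take a true related rate of 10% and an assumed independent HS rate b. The counted rate is 1 − 0.90 × (1 − b).
- b = 5%: counted rate 0.145, acceptance 60.4%.
- b = 10%: counted rate 0.19, acceptance 40.0%.

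The boundaries were set for related events, so an all-cause count cannot simply replace them.

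**Stopping statements side by side.**
- Section 4.1, General Design: stop at any Grade >3 toxicity, with no relatedness qualifier.
- Section 4.1, Interim Analysis: stop at Grade ≥3 in more than 2 patients, or any Grade 4, with no qualifier.
- Section 5.0, interim: stop at related Grade ≥3 in more than 1 patient, or if "any patient experiences grade 4 toxicity", the latter without a qualifier.
- Section 5.0, final: both the Grade ≥3 and the Grade 4 conditions are limited to related toxicity.

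The thresholds and the qualifiers both differ. With a stage 1 limit of more than 2 and the same final limit, acceptance would be 10.6% at 30% and 86.4% at 10%, so the stated characteristics belong to the Section 5.0 limits.

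**The case against.** A reader might infer that the committee is shut out of attribution and that the treating team decides it alone. The documents do not support that. They are silent on the assessor, and reviewing a Grade ≥3 event may well include judging its cause. The policy cited in Section 9 might also address the matter. At stage 1 the board evaluates the results and must approve continuation, and it can close accrual.

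Nor is attribution the only filter throughout: the Section 4.1 statements and the interim Grade 4 clause carry no relatedness qualifier. Adverse events are assessed before treatment and at every visit (Section 4.2), so each patient has a baseline. Section 5.0 also promises descriptive summaries for its outcomes in general terms. Finally, the misattribution shares are assumed, and the calculation supposes that review corrects none of the errors.

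All of this stands, and it limits the point to what is unspecified and unreported. It does not close the gap. The final verdict has no written board step. Nothing says that the interim results include events labelled unrelated. No all-cause Grade ≥3 figure is named.

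**Conclusion.** The concern holds in a limited form. The primary endpoint, the Section 5.0 Grade ≥3 counts and the only named toxicity proportion all rest on a relatedness judgement with no stated assessor or confirmation, and the planned output does not show its effect. The firm part is that one patient's label can change the outcome at either boundary, and that at true rates of 20% to 30% about 39% to 41% of trials would sit one patient beyond a limit. The rise in acceptance from 9.0% to between 14.5% and 32.1% is an illustration that depends on assumed misattribution of 10% to 30%. It is not evidence that attribution will be biased in this trial.

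**What to change.** 1. In Section 5.0, beside the treatment-related proportion, report the proportion of patients with any Grade ≥3 adverse event that is new or worse than at the pre-treatment assessment, in the primary window and regardless of attribution, with its exact 95% interval. Label it a sensitivity figure and leave the Section 5.0 boundaries unchanged.
2. List each Grade ≥3 event attributed to another cause. Send the listing to the DSMC with both the interim and the final results, and state in Sections 5.0 and 8.0 that the committee confirms attribution in the review it already performs.
3. Do not add a rule that events of uncertain cause count as related. The 60.4% and 40.0% figures above show that this could change the operating characteristics materially.
4. Reconcile the stopping statements in Section 4.1 (General Design and Interim Analysis) and Section 5.0, in both threshold and relatedness qualifier.

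The cost is some wording, one table row and one listing, from data already collected at each visit. The downside is that the all-cause figure may look less favourable, since it will include some events caused by the disease.

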#### 9.0 ADVERSE EVENTS

#### 9.1 Adverse Event Definitions

 AEs are defined as outlined by Albert Einstein College of Medicine's "Reportable Events Policy."[11]

# 9.2 Adverse Event Reporting

 AEs will be reported to the IRB as outlined by Albert Einstein College of Medicine's "Reportable Events Policy."

### 10.0 RISKS/BENEFITS

- Anticipated risks (medical, social, psychological, and/or legal)
  - This protocol is considered greater than minimal risk, due to radiation exposure and the skin biopsy procedure.
  - The initial risk of radiotherapy is temporary discomfort and inconvenience during the treatment period.
  - This dose of radiotherapy may cause temporary hair loss at the treatment site for a few months.
  - The risk of acute or chronic radiation-induced dermatitis is thought to be very low with the dose of radiotherapy being employed in this study.
  - A risk of low-intermediate dose radiation is Radiation Induced Cancer (RIC) such as skin cancer (BCC, SCC, melanoma)[2]. In patients treated for benign disease with intermediate dose radiotherapy (Range 3-50 Gy, mean approximately 20Gy), normal tissue side effects are rare or minimal. RIC risk is normally very small in adults (<1%) and decreases with increasing age.

  - o Blood draw may cause discomfort, pain, and bruising.
  - Risks from skin biopsy may include temporary pain during the procedure, a small chance of infection, and the possibility that biopsy leaves a small scar.
  - A psychological risk is that the treatment will not have any clinical improvement.
  - o Breach of confidentiality is a possible risk if data is lost or stolen.
- How anticipated risks will be minimized
  - To minimize RIC risks- careful body positioning during radiotherapy and shielding of tissues outside of the intended treatment field will be

- employed in a customized fashion for each patient. In most cases, treatment with superficial forms of radiotherapy (electrons or surface brachytherapy) will be employed to minimize the volume of tissue irradiatied.
- Lab tests and skin biopsy will be performed carefully, using standard safety measures.
- o Confidentiality will be maintained as described in Section 7.1.
- Potential benefits
  - Potential benefits include disease improvement and potential remission, along with improved quality of life

# **12.0 APPENDICES**

# Appendix A: Photos

Persistent HS Hurley Stage 3 Lesions on the buttocks of two patients.

# Appendix B: Relevant Skin and Subcutaneous Tissue CTCAE Items[6]

Skin and Subcutaneous Tissue Disorders							
		G	Grade				
Adverse Event	1	2	3	4	5		
Bullous dermatitis	Asymptomatic; blisters covering	Blisters covering 10 - 30% BSA; painful blisters; limiting instrumental ADL	Blisters covering >30% BSA; limiting self care ADL	Blisters covering >30% BSA; associated with fluid or electrolyte abnormalities; ICU care or burn unit indicated	Death		
Dry Skin	Covering <10% BSA and no associated erythema or pruritus	Covering 10 - 30% BSA and associated with erythema or pruritus; limiting instrumental ADL	Covering >30% BSA and associated with pruritus; limiting self care ADL				
Pain of Skin	Mild pain	Moderate pain; limiting instrumental ADL	Severe pain, limiting self care				
Pruritus	Mild or localized; topical intervention indicated	Intense or widespread; intermittent; skin changes from scratching (e.g., edema, papulation, excoriations, lichenification, oozing/crusts); oral intervention indicated; limiting instrumental ADL	Intense or widespread; constant; limiting self care ADL or sleep; oral corticosteroid or immunosuppre ssive therapy indicated				
Skin hyperpigme ntation	Hyperpigmentation covering <10% BSA, no psychosocial impact	Hyperpigmentati on covering >10% BSA; associated psychosocial	-				

		impact			
Skin hypopigme ntation	Hypopigmentation or depigmentation covering <10% BSA; no psychosocial impact	Hypopigmentation or depigmentation covering >10% BSA; associated psychosocial impact			
Skin induration	Mild induration, able to move skin parallel to plane (sliding) and perpendicular to skin (pinching up)	Moderate induration, able to slide skin, unable to pinch skin; limiting instrumental ADL	Severe induration, unable to slide or pinch skin; limiting joint movement or orifice (e.g., mouth, anus); limiting self care ADL	Generalized; associated with signs or symptoms of impaired breathing or feeding	Death
Skin ulceration	Combined area of ulcers <1 cm; nonblanchable erythema of intact skin with associated warmth or edema	Combined area of ulcers 1 - 2 cm; partial thickness skin loss involving skin or subcutaneous fat	Combined area of ulcers >2 cm; full-thickness skin loss involving damage to or necrosis of subcutaneous tissue that may extend down to fascia	Any size ulcer with extensive destruction, tissue necrosis, or damage to muscle, bone, or supporting structures with or without full thickness skin loss	

# Appendix C: PROMIS - Pain Interference

PROMIS Item Bank v1.0 - Pain Interference - Short Form 8a

#### Pain Interference - Short Form 8a

Please respond to each question or statement by marking one box per row.

#### In the past 7 days...

-	1 (1987) (1981) (1984) (1984) (1984) 1 (1987) (1987) (1984) (1984) (1987)	Not at all	A little bit	Somewhat	Quite a bit	Very much
PROM	How much did pain interfere with your day to day activities?	 		0		
PROMINGE 2	How much did pain interfere with work around the home?		2			5
PRODUCT à	How much did pain interfere with your ability to participate in social activities?		2	3	0	5
PROINS 4	How much did pain interfere with your enjoyment of life?					5
PRINTE 5	How much did pain interfere with the things you usually do for fun?					
PKNIN30 5	How much did pain interfere with your enjoyment of social activities?		2	3		5
PRININGA F	How much did pain interfere with your household chores?		2	3		5
PRODUCTS 8	How much did pain interfere with your family life?					D ,

Investigator Format © 2008-2012 PROMIS Health Organization and PROMIS Cooperative Group Page 1 of 1

# **Appendix D: PROMIS- Physical Functioning**

#### PROMIS SF v1.0 - Physical Function 12a

#### **Physical Function – Short Form**

#### Please respond to each item by marking one box per row.

stand an "Suppo walking people.	lowing questions ask about your ability to nd move with and without support. rt" means using items such as canes, g sticks walkers and leg braces, or other	Yes	No	)			
PF Screencr 2	Can you walk 25 feet on a level surface (with or without support)?			J			
			articipant re articipant sl		tems o PFB5 and	proceeds	o PFA55
			Without any difficulty	With a little difficulty	With some difficulty	With much difficulty	Unable to
PFC8	Are you able to walk a block on flat grou	ınd?	5	4	3	2	1
PFC20	Are you able to walk up and down two st	to walk up and down two steps?		4	3	2	
PFA39	Are you able to run at a fast pace for two	ou able to run at a fast pace for two miles?		□ 4	3	2	
PFA25	Are you able to do yard work like raking weeding, or pushing a lawn mower?	leaves,	5	4	3	2	
			Not at all	Very little	Somewhat	Quite a lot	Cannot do
PF87	Does your health now limit you in doing strenuous activities such as backpacking, playing tennis, bicycling or jogging?	skiing,	5	4	3	2	I I
PFB5	Does your health now limit you in hiking couple of miles on uneven surfaces, inclubills?		5		☐ 3	2	
			Without any difficulty	With a little difficulty	With some difficulty	With much difficulty	Unable to do
PFA55	Are you able to wash and dry your body:	,	5	4	3	2	
PFCSS	Are you able to get in and out of bed?		□ .s	4	3	2	
PFA9	Are you able to bend down and pick up of from the floor?	lothing	s				

Investigator Format © 2008-2012 PROMIS Health Organization and PROMIS Cooperative Group

Page 1 of 2

# PROMIS SF v1.0 - Physical Function 12a

		Without any difficulty	With a little difficulty	With some difficulty	With much difficulty	Unable to
PFA12	Are you able to push open a heavy door?	5		3	2	
PF_28	Are you able to reach and get down an object (such as a can of soup) from above your head?	5		3	2	
		Not at all	Very little	Somewhat	Quite a lot	Cannot do
PFC35	Does your health now limit you in doing eight hours of physical labor?	5	4	3	2	

Investigator Format © 2008-2012 PROMIS Health Organization and PROMIS Cooperative Group

# Appendix E: DLQI

## DERMATOLOGY LIFE QUALITY INDEX

Hosp	ital No:	Date:			DLQI
Name Addr	. .	Diagnosis:	Score	:	
The :	aim of this questionnaire is to R THE LAST WEEK. Please tic	measure how much y		em has	affected your lif
1.	Over the last week, how itchy painful or stinging has your sbeen?		Very much A lot A little Not at all		
2.	Over the last week, how emba or self conscious have you be of your skin?		Very much A lot A little Not at all		
3.	Over the last week, how much skin interfered with you going shopping or looking after your garden ?	·	Very much Λ lot A little Not at all		Not relevant □
4.	Over the last week, how much skin influenced the clothes you wear?	has your	Very much A lot A little Not at all		Not relevant □
5.	Over the last week, how much skin affected any social or leisure activities?	has your	Very much A lot A little Not at all		Not relevant ⊓
6.	Over the last week, how much skin made it difficult for you to do any sport ?	has your	Very much A lot A little Not at all		Not relevant □
7.	Over the last week, has your s you from working or studying		Yes No		Not relevant □
	If "No", over the last week how your skin been a problem at work or studying?	much has	A lot A little Not at all		
8.	Over the last week, how much skin created problems with yo partner or any of your close for relatives?	ur	Very much A lot A little Not at all		Not relevant □
9.	Over the last week, how much skin caused any sexual difficulties ?	has your	Very much A lot A little Not at all		Not relevant □
10.	Over the last week, how much problem has the treatment fo skin been, for example by malyour home messy, or by taking	r your King 3 up time?	Very much A lot A little Not at all		Not relevant □
®AY F	Please check you nlay, GK Khan, April 1992 www.dcrmatolo	have answered EVEF ogv.org.uk, this must not be e			

21

